Study Title: Spinal Epidural Electrode Array to Facilitate Standing and Stepping after Spinal Cord Injury

NCT Number: NCT02339233

Document Date: August 8, 2017

Final protocol

A. Background, including a brief literature review:

Spinal cord epidural stimulation (SCES) has been applied alone in a number of individuals with clinically complete spinal cord injury (SCI), showing that some alternating stepping-like actions can be induced [1]. SCES has been used in combination with repetitive stepping on a treadmill for facilitation of walking-like movements after an incomplete lesion in two individuals showing stepping could be sustained for a longer period of time with less effort in the presence of SCES [2]. This report provides promising results of a combination of locomotor training and SCES. In contrast to our presently proposed studies on clinically complete SCI research participants, the previously reported studies included patients with incomplete injuries who already had some stepping ability before treatment [3]. Several recent findings suggest that a combination of SCES and locomotor training in individuals with clinically complete SCI could be very successful for the recovery of standing and walking. Locomotor-like patterns can be facilitated by SCES in complete spinally transected rats [4], cats [5], and humans with clinically complete SCI [6]. However, the long-term functional changes that occur in the spinal cord after clinically complete SCI have not been comprehensively examined, and it is likely to require more complex and adaptive stimulation protocols in order to achieve optimal results. A key to successful broad application of SCES to the majority of individuals with chronic SCI and other neurological disorders including multiple sclerosis, brain injury, stroke, and Parkinson's disease may be a functionally-adaptive site-specific stimulation. However, this capability will require a more advanced multi-electrode array technique which we are currently developing in preparation for the second phase of our long-term plans. The current proposal is a pilot study including 10 research participants with clinically complete SCI who will undergo epidural electrode implantation for spinal cord stimulation and locomotor training to improve standing and stepping with the combination of epidural stimulation and locomotor training; and to provide critical information for the development of more advanced electrodes.

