We propose that daily locomotor training in the presence of SCES will enable the individual with clinically complete SCI to stand and step independently while bearing full weight. Non-patterned electrical stimulation of the lumbar spinal cord can induce patterned, locomotor-like activity in individuals with clinically complete SCI [1]. Modifying the frequency of stimulation can induce extensor patterns similar to that observed during standing [45]. In addition, when afferent information is also provided there is further modulation of these motor patterns elicited by epidural stimulation [46]. Individuals with a clinically complete spinal cord injury can execute independent steps using a body weight support system on a treadmill (BWST) using manual assistance without epidural stimulation. When combined with SCES, we anticipate the training will be even more successful, enabling prolonged periods of independent stepping and standing. Although there will not be a separate control group studied simultaneously, historical controls will consist of the best stepping and standing performance that have been observed previously in our laboratory in individuals that have a clinically complete SCI. Performance beyond this threshold by any individual treated with both epidural stimulation and training will be interpreted as a significantly better intervention than training alone.

Future studies will eventually focus on development and implementation of the more advanced multi-electrode array technique that will provide functionally-adaptive site-specific stimulation. The adaptive stimulation strategy proposed here takes advantage of capabilities of our new array design that are not possible using either conventional or commercially available electrode arrays. Our future arrays will provide two key benefits:

- Our electrode arrays cover a larger area than commercially available arrays, extending from the midthoracic to the sacral extents of the spinal cord. It is possible that the optimal stimulation sites for facilitating stepping versus standing may be spatially distinct on the spinal cord. If this is the case, conventional arrays are less likely to be able to recover both stepping and standing in the same patient.

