These individuals will not be concurrently enrolled in any other experimental studies unless approved by the principal investigator. Each research participant will be given a coded identification number to designate all evaluations. We will retain the data for reporting to granting agencies even when the individual is not eligible for the study. This data will be stored by the coded identification number without information identifying the individual.

We will evaluate the research participants for: 1) functional neurophysiological assessment (FNPA); 2) somatosensory evoked potentials (SEP); 3) sympathetic skin responses (SSR); 4) efferent motor activity during standing; 5) efferent motor activity during stepping; 6) reflexes during supine, prone, sitting and standing; 7) bladder function; and 8) cardiovascular function. Each of these measurements will take between 1 and 4 hours. The FNPA, SEP and SSR will be performed while the research participant is lying supine on a mat. The efferent motor assessments will be performed in the body weight support treadmill with the assistance of trainers at the hip and at each leg.

We will assess metabolic parameters, inflammatory markers, complete blood count, bone density and health markers, blood glucose control and drug toxicity panel. A trained

technician will draw a venous blood sample. Participants may undergo a 12-hour fast the night before, including no food or drink including alcohol or caffeine (water is permitted). A comprehensive drug screen by urinalysis will be done to assess the use of illicit drugs. These blood and urine analyses may be repeated periodically throughout the course of the study. A blood sample will be stored for batch processing at the end of the study (for participants that complete the screening process).

After completion of these evaluations, participants will undergo 80 sessions of step/stand training. We will repeat experiments after the completion of the 80 training sessions to quantify that no motor pattern changes are achievable with locomotor training alone. Drs. [name], [name] and [name] will meet to discuss the results of the preliminary testing and evaluate if the participant is eligible for surgical implantation for SCES.

FULL ENROLLMENT: Surgery + Epidural Stimulation + Training (2nd consent)

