[name] and the research team might ask the participant to return for training in the laboratory for extended periods of 80-200 sessions post participation in the original sessions. Training (stand or step) will be designed to optimize parameters and built to improve on previous training. During this time participants might be asked to functional train with the combination of our adaptive epidural stimulation strategy with manual locomotor training. During training, the participants will be provided with ES using the parameters determined using the computation learning method which is developed during phase 2 described below.

E. How the study population is determined and how they will be equitably recruited

There are approximately 250,000 Americans with a SCI. Of this population, 82% are male. Fifty-six percent of the injuries occur in people between the ages of 16 and 30, and the average age of an individual who has sustained a SCI is thirty-one. Thirty-eight percent of the research participants studied will be derived from a population of minorities (African-American, American Indian or Alaskan Native, Asian, Hispanic or Latino, and Native Hawaiian or other Pacific Islander). Every effort will be made to recruit women, though only about 18% of SCI patients are female. Although many people after a SCI have secondary health issues such as spasticity and frequent urinary tract infections, they are otherwise healthy individuals. Standing and stepping is considered beneficial for people with SCI who are confined to a wheelchair, as immobilization can contribute to secondary pathologies such as osteoporosis, leg muscle contractures, decreased cardiovascular health, pressure sores and muscle atrophy. Children will not be studied. Pregnant women with SCI will not be studied because the risks to the fetus are unknown. No other vulnerable research participants will be included.

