All research participants, irrespective of age or sex, will meet the following criteria: 1) stable medical condition without cardiopulmonary disease or dysautonomia that would contraindicate standing or stepping with BWST; 2) no painful musculoskeletal dysfunction, unhealed fracture, contracture, pressure sore, or urinary tract infection that might interfere with stand or step training; 3) no clinically significant depression or ongoing drug abuse; 4) no current anti-spasticity medication regimen; 5) non-progressive SCI above T10; 6) must not have received botox injections in the prior six months; 7) be unable to stand and step independently overground; 8) unable to voluntarily move all individual joints of the legs; 9) at least one-year post injury; and 10) must be at least 18 years of age. In addition, all subjects must satisfy each of the three conditions of the functional neurophysiological assessment described below.

Additionally, research participants with the following characteristics will not undergo any assessments using transcranial magnetic stimulation (TMS): 1) metal in head (except mouth) such as but not limited to cochlear implant, implanted brain stimulators, aneurysm clips; 2) increased intracranial pressure (which lowers seizure thresholds); 3) cardiac pacemakers; 4) implanted medication pumps; 5) intracardiac lines; 6) significant heart disease; 7) history of stroke or other brain lesions; 8) personal or family history of epilepsy; 9) receiving tricyclic antidepressants or neuroleptics (which lower seizure threshold); 10) heavy alcohol consumption within past 48 hours

Functional Neurophysiological Assessment (FNPA). We will use FNPA to screen potential research participants based on specific neurophysiological inclusion criteria. Participants must have no volitional control of movement below the level of the lesion, but must retain some brain influence on spinal reflexes. Our target population, which will be identified by FNPA, cannot be identified reliably using traditional assessments: hence individual subjects may be classified widely as Class A, B, or C on the ASIA SCI scale. We will include only subjects who fulfill the following three requirements:

1. There is no descending volitional control of movement below the lesion
2. Segmental reflexes remain functional below the lesion
3. Brain influence on spinal reflexes is retained

G. Design/methodology including all survey instruments, questionnaires, etc.

SCREENING CONSENT:

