Following post-surgery experiments, training will be conducted 5 times per week for 160 sessions on an outpatient basis. In Stage 2 the individuals will be seen in our laboratory on a daily basis for testing and training. After the initial 20 sessions of training, they might be asked to come train twice a day (stand and step on the same day) with a 2-4 hour resting period in between. We will evaluate the combination of epidural stimulation with manual step (locomotor) training. This stage will be conducted over four to eight months. Periodically, blood and urine samples may be collected, processed for testing as described above, and stored for batch testing at the end of the study period.

During training, the patients will be provided with epidural stimulation using the parameters defined in Stage 1.

In certain cases, the physician, [name], might recommend a specific training change or limit on sessions to mitigate risk for research participant. Any special considerations are specified in the addendum section.

The participants may be evaluated weekly for 1) efferent motor activity during standing and stepping and 2) reflexes during supine, prone, sitting and standing, as described above.

Home Training: Following the determination of optimal parameters for standing or voluntary activity, the participant might be given a Patient Programmer (Medtronic Model 37743) to translate weight bearing and stand training and/or voluntary movement with stimulation to the home environment and perform additional training. The programmer will be optimally programmed by the research team in such a way to restrict configuration changes by research participant. A pre-determined range of optimal voltages will be accessible by the research participants. A very specific protocol for stimulation and training will be given by the research team and the participant will be required to complete a training log. The research team will collect the home training log from the participant once a week and evaluate the need for changes to the home-based training protocol.

Stage 2B: Adaptive Multielectrode Epidural Stimulation and Locomotor Training

Stage 2 will evaluate the combination of our adaptive epidural stimulation strategy with manual step (locomotor) training. During training, the participants will be provided with ES using the parameters determined using the computation learning method in Phase 1.

Experimental materials.

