These results will reveal whether conventional electrodes can be used to facilitate stepping in clinically complete spinal cord injury patients. This study will clarify whether the optimal spinal cord sites for using epidural stimulation to induce stepping and standing migrate over the course of training in the human spinal cord. We expect that these data will provide further evidence of the plasticity of the injured spinal cord, and that training modifies the spinal networks for stepping. Stepping performance of the patients will be compared against historical controls that were given step training without epidural stimulation. The criteria for success of the combined treatment will be determined by the best outcomes that have been obtained for previous patients who were only trained.

h. Treatment regimen(s) (*for medically invasive research*)

i. Clinical information (when applicable) (*for medically invasive research*)

j. Statistical analysis of the collected data

No statistical analysis will be used for comparison of data. This study is designed as a proof of principle study without statistical power to demonstrate the feasibility of the methods.

k. Data and Safety Monitoring Plan

Entity responsible for monitoring is identified:

The study will be monitored by a Data Safety Monitoring Board consisting of: [name] (Neurosurgeon), [name] (physiatrist); [name]

[name] (cardiologist) and [name] (Urologist) who are not associated with the study.

Policies and procedures for adverse event reporting are described:

If a subject develops an adverse event it will be reported to the DSMB, local IRB and Sponsor within 24 – 48 hours of being notified of the event.

Protocol Compliance:

Any deviations in the protocol will be documented and reported to the IRB.

Plans for measuring appropriate intervals between safety reviews and predetermined criteria for stopping the study:

Research participants will be continuously monitored for complications, adverse events and/or serious adverse events. If any complications arise during the course of the study the local Medical Advisor ([name]) will be notified. All study procedures will be halted until the complication, adverse event and/or serious adverse event has been reviewed by the medical advisor and it has been determined that it is safe for the study participant to return to participating in study procedures.

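### One participant out of ten beating the laboratory's best past result is to be read as superiority over training alone, with no control of the false-positive rate and in conflict with the stated unpowered, proof-of-principle design

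*Protocol*

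**What the plan says.** The study has one arm: "The current proposal is a pilot study including 10 research participants with clinically complete SCI". Section A says there is no concurrent control group. The historical control is the best stepping and standing seen before in the same laboratory in people with clinically complete injury. The decision rule follows: "Performance beyond this threshold by any individual treated with both epidural stimulation and training will be interpreted as a significantly better intervention", the comparison being with training alone.

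The end of section G repeats the benchmark: "The criteria for success of the combined treatment will be determined by the best outcomes that have been obtained for previous patients", meaning patients who received training only. Section j then says that data will not be compared statistically, and adds: "This study is designed as a proof of principle study without statistical power to demonstrate the feasibility of the methods".

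Four other places bear on the rule:

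- Section D (Screening) has 80 training-only sessions before implantation, with testing repeated afterwards to "quantify that no motor pattern changes are achievable with locomotor training alone".
- Stage 2A says "training will be conducted 5 times per week for 160 sessions on an outpatient basis", with optional weekly evaluation.
- Section D (Follow-up) says participants might be asked to "return for training in the laboratory for extended periods of 80-200 sessions post participation in the original sessions".
- Section F (FNPA) requires participants to have "no volitional control of movement below the level of the lesion, but must retain some brain influence on spinal reflexes".

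**The concern.** The rule sets one maximum against another. The largest of several observations in one group will often exceed the largest in a second group for no reason other than chance, and more often when the second group is small. The protocol gives neither the number of past patients nor a numeric threshold, so the reader cannot tell how likely a success is when stimulation contributes nothing.

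The conclusion also does not fit the stated purpose. A study that disclaims statistical comparison and power can show that something is possible in one person. It cannot conclude that one intervention is significantly better than another.

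The rule is loose in other respects. It names no scale and no time at which the threshold is applied, and optional further training after the planned sessions leaves the window for an exceedance open. Each participant's own training-only result is measured but not used. The past patients are described only as clinically complete. They are not stated to meet the FNPA condition of retained brain influence, so the direction and size of any comparator bias are unknown.

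At stake is the trial's only stated efficacy conclusion, and it concerns a surgically implanted device.

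**Working it through.** The protocol states no error rate, power or sample-size calculation, so there is no figure to reproduce. The check works out how the rule behaves when stimulation has no effect.

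**Inputs.** n = 10 treated participants (sections A and F). Success means at least one of them passes the best past result (section A). The number of past patients, m, is not given and is varied as an assumption.

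**1. One outcome, continuous scale.** Assume that the 10 participants and m past patients are exchangeable and equally tested. The overall best performer is then equally likely to be any of the 10 + m people, so

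P(success with no effect) = 10/(10 + m).

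**2. Either standing or stepping counts.** With p = 10/(10 + m), the rate lies between p (perfectly correlated outcomes) and 1 − (1 − p)² (independent outcomes). At m = 10 the upper value is 1 − 0.5² = 0.75. A bivariate normal simulation with correlation 0.8 falls between the two.

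| Assumed m | One outcome | Either, correlation 0.8 | Either, independent |
|---|---|---|---|
| 5 | 67% | 80% | 89% |
| 10 | 50% | 65% | 75% |
| 50 | 17% | 26% | 31% |
| 100 | 9% | 15% | 17% |

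For one outcome to reach 5%, solve 10/(10 + m) = 0.05, which gives m = 190.

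**3. Ties.** If performance is a coarse count, ties at the top do not count as exceeding, and the rate falls. With illustrative Poisson counts of mean 0.5 to 1 (assumed), it is 31–34% at m = 10, 8–9% at m = 50 and 4–5% at m = 100.

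**4. Fixed threshold.** Suppose each participant has chance p0 of passing with no stimulation effect. Then P(success) = 1 − (1 − p0)^10. With p0 = 1%, 2% and 5% (assumed) this is 9.6%, 18.3% and 40.1%. Holding the rule to 5% needs p0 = 1 − 0.95^(1/10) = 0.51% or less.

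**5. What one exceedance shows.** Exact (Clopper–Pearson) 95% intervals for x of 10 are 0 to 30.8% for x = 0, 0.3% to 44.5% for x = 1, and 6.7% to 65.2% for x = 3. One success leaves the frequency of exceedance almost unknown.

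**6. Is a training-only success plausible?** Sections A's own account says it is not ruled out: training without stimulation can produce some independent steps and brief full-weight-bearing standing.

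**The case against.** The strongest objection is that participants are not exchangeable with past patients. Implantation follows 80 training-only sessions and an investigator decision, so people who respond well to training may be excluded. This can be illustrated. Assume normal scores, only the lower half after the run-in implanted, and a correlation of 0.5 or 0.8 between run-in and later no-effect performance. The rate at m = 10 then falls from 50% to about 25% or 6%, and at m = 50 from 17% to about 4% or 0.2%. This stands as a caution against the higher figures. It is not error control, because the protocol gives no numeric selection rule and no such correlation. The extra sessions and repeated testing could push the other way.

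A second objection is that this is a pilot, that the sentence sits in the background section, and that its wording names no test or significance level. Showing that one person can do what no trained-only patient has done is ordinary proof-of-principle reasoning. That supports reporting the exceedance. It does not support concluding that the intervention is significantly better, and the end of section G adopts the same benchmark as the criterion for success.

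Other points have some weight. Thresholds, assessment time and a description of the controls could be placed in an analysis plan that is not at hand. Later training is optional and not tied to the rule. Fewer than ten may be implanted, which would lower the rate. Sections D and G (Stage 1C) also provide for testing with and without stimulation after surgery, a within-person contrast that bears more directly on what stimulation adds and that the rule ignores. None of this removes the fault, because the protocol itself fixes the superiority conclusion.

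**Conclusion.** The concern holds and must be fixed. Followed as written, the plan turns one exceedance by one person into a claim of superiority over training alone, while section j disclaims the statistical comparison and power that such a claim needs.

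The false-positive rate cannot be derived, because neither m nor the chance of passing under training alone is given. Under exchangeability, equal testing and a continuous scale it runs from 67% (m = 5) to 9% (m = 100) for one outcome, and higher if either outcome counts. Ties or selection after the run-in could bring it well below these values. The firm conclusion is that the rate is uncontrolled and unknown; no single figure is established.

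**What to change.** 1. In section A, delete the sentence that reads an exceedance by any individual as superiority. State instead that the number of implanted participants exceeding the best training-only performance will be reported descriptively, with no claim of superiority.
2. Align the success criterion at the end of section G with this.
3. Before analysis, fix the numeric standing and stepping thresholds. State m, how the past patients were selected and tested, how many sessions they had, and whether they met the FNPA conditions.
4. Name one assessment time for applying the thresholds, for example the end of the 160 post-implant sessions.
5. For each threshold, report the number exceeding it out of all implanted participants (planned ten) with an exact 95% interval. Beside it, list each participant's own result after the 80 training-only sessions, noting that the later result also reflects further training.

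Do not substitute a rule requiring some minimum number of the ten: its error rate would depend on the same unknowns.

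The cost is protocol wording and a tabulation of control and run-in data that already exist or are already planned. No new patients, tests or procedures are needed. The drawback for the sponsor is that success becomes harder to claim.
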